## 5.2. Exclusion Criteria

A subject will not be eligible for inclusion in this study if any of the following criteria apply:

[1] CONCURRENT CONDITIONS/MEDICAL HISTORY (INCLUDES LIVER FUNCTION AND QTc INTERVAL)

 
1. Pregnant or lactating women.
 
2. History of other inflammatory rheumatological or autoimmune disorders, other than Sjögren's syndrome secondary to RA.
 
3. History of any respiratory disease which (in the opinion of the investigator) would compromise subject safety or the ability of the subject to complete the study (e.g. significant interstitial lung disease, such as pulmonary fibrosis, chronic obstructive pulmonary disease (COPD), moderate-severe asthma, bronchiectasis, previous PAP).
 
4. Clinically-significant or unstable (in the opinion of the investigator) persistent cough or dyspnea that is unexplained.
 
5. QTc >450msec or QTc >480msec for subjects with bundle branch block. The QTc is the QT interval corrected for heart rate according to Fridericia's formula (QTcF).
 
6. Liver function tests: alanine aminotransferase (ALT) >1.5x upper limit of normal (ULN); aspartate transaminase (AST) >1.5 upper limit of normal; alkaline phosphatase and bilirubin <math>\geq</math>1.5xULN (isolated bilirubin >1.5xULN is acceptable if bilirubin is fractionated and direct bilirubin <35%).
 
7. Current active liver or biliary disease (with the exception of Gilbert's syndrome or asymptomatic gallstones or otherwise stable chronic liver disease per investigator assessment).
 
8. Significant unstable or uncontrolled acute or chronic disease (e.g., cardiovascular including uncompensated congestive cardiac failure NYHA III or IV, myocardial infarction within 12 months, unstable angina pectoris, uncontrolled hypertension, uncontrolled hypercholesterolemia) pulmonary, hematologic, gastrointestinal (including Crohn's Disease or ulcerative colitis), hepatic, renal, neurological, psychiatric, malignancy, endocrinological or infectious diseases, which, in the
 

opinion of the investigator, could confound the results of the study or put the subject at undue risk.

9. A history of malignant neoplasm within the last 10 years or breast cancer within the last 20 years, except for non-melanoma skin cancers that have been excised and cured or carcinoma *in situ* of the uterine cervix.
10. Kidney disease: Current or history of renal disease, or estimated creatinine clearance <60 mL/min/1.73m^2 or serum creatinine >1.5xULN within 28 days of Day 1.
11. Hereditary or acquired immunodeficiency disorder, including immunoglobulin deficiency.
12. History of infected joint prosthesis at any time, with the prosthesis still *in situ*. History of leg ulcers, catheters, chronic sinusitis or recurrent chest or urinary tract infections.
13. Active infections, or history of recurrent infections (excluding recurrent fungal infections of the nail bed), or have required management of acute or chronic infections, as follows:
  - a. Currently on any suppressive therapy for a chronic infection (such as tuberculosis, pneumocystis, cytomegalovirus, herpes simplex virus, herpes zoster and atypical mycobacteria).

OR

- b. Hospitalization for treatment of infection within 26 weeks of Day 1.

OR

- c. Use of parenteral (IV or IM) antimicrobials (antibacterials, antivirals, antifungals, or antiparasitic agents) within 26 weeks of Day 1 or oral antimicrobials within 14 days of Day 1.

14. A vaccination (live or attenuated) within 30 days of Day 1 or BCG vaccination within 365 days of Day 1, or a live vaccination planned during the course of the study.
15. Any surgical procedure, including bone or joint surgery/synovectomy within 12 weeks prior to Day 1 or any planned surgery within the duration of the study or follow-up period.
16. For those subjects in the actigraphy substudy:
  - wheelchair, walking aids, artificial limbs
  - history of severe skin allergy
  - active implantable device
  - pacemaker.

## [2] CONCOMITANT MEDICATIONS

17. Use of prohibited medications:

**Prior to AND throughout the study:**

- Any conventional DMARDs other than MTX (including hydroxychloroquine,

sulphasalazine, minocycline, ciclosporin) should be withdrawn at least 2 weeks prior to Day 1.

- Subjects may require longer to discontinue azathioprine or leflunomide prior to randomization:
  - Azathioprine must be discontinued  $\geq$ 28 days prior to randomization.
  - Leflunomide must be discontinued  $\geq$ 12 weeks prior to randomization (or  $\geq$ 14 days after 11 days of standard cholestyramine or activated charcoal washout).
- **For these subjects, written informed consent for the study (or sub-studies) must be obtained prior to beginning the screening period.** However, other screening assessments, other than consent, must occur within 28 days prior to randomization.
- Any biologic agents (such as TNF inhibitors such as adalimumab, etanercept, infliximab, certolizumab pegol, golimumab or non-TNF inhibitors (including abatacept, rituximab, tocilizumab, belimumab).
- Any anti-rheumatic investigational compounds.
- Any alkylating agents (such as cyclophosphamide or chlorambucil).
- Plasmapheresis or intravenous immunoglobulin (IVIG) within 26 weeks of Day 1.

18. Corticosteroids:

- Any IM, IV or IA corticosteroids within 8 weeks of Day 1.
- Oral corticosteroids:
  - Any treatment with  $>10$  mg/day dose oral prednisolone (or equivalent) within 28 days of Day 1.
  - New oral corticosteroid or changes in corticosteroid dose within the 28 days prior to Day 1. (New topical steroids and immunosuppressive agents (e.g., eye drops, creams) are permitted).

19. Non-steroidal anti-inflammatory drugs (NSAIDs):

- New or change in dose of NSAID within 14 days of Day 1.

20. Any non-anti-rheumatic investigational treatment must be discontinued for at least 4 weeks or 5 half-lives, whichever is longer, prior to Day 1.

#### [3] RELEVANT HABITS

21. Have current drug or alcohol abuse or dependence, or a history of drug or alcohol abuse or dependence within a year prior to Day 1.

#### [4] CONTRAINDICATIONS

22. History of sensitivity to any of the study treatments, or components thereof or a history of drug or other allergy that, in the opinion of the investigator or Medical

Monitor, contraindicates their participation.
---

[5] DIAGNOSTIC ASSESSMENTS AND OTHER CRITERIA
23. Abnormal chest X-ray within 12 weeks of Day 1 (locally read and reported by a radiologist) judged by the investigator as clinically-significant.
24. Any Grade 3 or 4 hematology or clinical chemistry laboratory abnormality [CTCAE, 2009 v4.0] within 28 days of Day 1.
25. Hemoglobin $\leq 9$ g/dL; white blood cell count $\leq 3.0 \times 10^9/L$ ; platelet count $\leq 100 \times 10^9/L$ ; absolute neutrophil count $\leq 1.5 \times 10^9/L$ ; lymphocyte count $\leq 0.5 \times 10^9/L$ within 28 days of Day 1.
26. Serologic evidence of current/previous Hepatitis B virus (HBV) infection based on the results of testing for Hepatitis B surface antigen (HBsAg) and anti-Hepatitis B core (anti-HBc) antibody as follows within 28 days of Day 1:

 
Subjects positive for HBsAg and/or positive for anti-HBc antibody (regardless of anti-HBs antibody status) are excluded.
 

27. Hepatitis C: Positive test for Hepatitis C virus (HCV) antibody confirmed on a subsequent blood sample by RNA-PCR assay within 28 days of Day 1.

 
Subjects who are positive for Hepatitis C antibody and negative when the Hepatitis C RNA-PCR assay is performed on a subsequent sample will be eligible to participate. Subjects who are positive for Hepatitis C antibody and have a positive result for the HCV when the Hepatitis C RNA-PCR assay is performed on the subsequent sample will not be eligible to participate.
 

28. Positive serology for human immunodeficiency virus (HIV) 1 or 2 (within 28 days of Day 1).

### 5.3. Screening/Baseline Failures

Screen failures are defined as subjects who consent to participate in the clinical trial but are never subsequently randomized. In order to ensure transparent reporting of screen failure subjects, meet the Consolidated Standards of Reporting Trials (CONSORT) publishing requirements, and respond to queries from Regulatory authorities, a minimal set of screen failure information is required including Demography, Screen Failure details, Eligibility Criteria, and any Serious Adverse Events.

#### 5.3.1. Re-Screening

If a subject has not met all of the Eligibility Criteria within the 28 day screening period, re-screening is required. Subjects are only allowed to be re-screened once; the entire screening process must be repeated (with the exception of chest X-ray if within 12 weeks of the first screening period or HRCT if this was already performed within the first screening period).

If a blood sample has to be withdrawn due to sample handling problems, breakage or sample integrity, this is not considered a re-screening.

Further details regarding the procedure for re-screening may be found in the SRM.

### **5.3.2. Re-Testing**

#### **5.3.2.1. Laboratory tests**

If a subject fails any of the laboratory exclusion criteria, the test may be repeated twice within the screening period. If the subject fails the laboratory criteria for a third time they will be considered a screen failure; these subjects may be re-screened as described in Section 5.3.1.

If a blood sample has to be withdrawn due to sample handling problems, breakage or sample integrity, this is not considered a re-testing.

Further details regarding the procedure for laboratory re-testing may be found in the SRM.

#### **5.3.2.2. $D_{LCO}$ test**

If the screening  $D_{LCO}$  value is  $\geq 70\%$  predicted, but the subsequent “Day 1” value is  $< 70\%$  but  $\geq 60\%$  predicted, the  $D_{LCO}$  test may be repeated if still within the screening window. If the repeat value is  $\geq 70\%$ , the “Day 1” activities may be completed, but if the value is again  $< 70\%$ , dosing must be postponed and a chest HRCT performed. If this cannot be done within the screening window, then the subject must be re-screened.

#### **5.3.2.3. ECG test**

The ECG may be repeated once within the screening period if the recorded QTcF value was slightly out of range, and the Investigator does not consider that there are any other clinically-significant ECG abnormalities that would preclude the subject from participating in the study.

### **5.4. Withdrawal/Stopping Criteria**

The following actions must be taken in relation to a subject who fails to attend the clinic for a required study visit:

- The site must attempt to contact the subject and re-schedule the missed visit as soon as possible.
- The site must counsel the subject on the importance of maintaining the assigned visit schedule and ascertain whether or not the subject wishes to and/or should continue in the study.
- In cases where the subject is deemed ‘lost to follow up’, the investigator or designee must make every effort to regain contact with the subject (where possible, 3 telephone calls and if necessary a certified letter to the subject’s last known mailing address or local equivalent methods). These contact attempts should be documented in the subject’s medical record.

- Should the subject continue to be unreachable, only then will he/she be considered to have withdrawn from the study with a primary reason of “Lost to Follow-up”.

Any subject that fails to achieve EULAR good/moderate response at Week 36 will not be dosed at Week 38, and will be withdrawn from the study; no further study treatment will be administered. A notification that the subject must be withdrawn will be sent to the investigator prior to the scheduled Week 38 visit.

A subject may withdraw from study treatment at any time at his/her own request, or may be withdrawn at any time at the discretion of the investigator for safety, behavioural or administrative reasons.

**In addition, study medications will be discontinued and the subject withdrawn from the study in the event of any of the following:**

- All serious infections.
- Pregnancy.
- Confirmed PAP.
- Severe or serious hypersensitivity reactions, including anaphylaxis.
- If the liver chemistry stopping criteria (Section 5.4.1) or QTc stopping criteria (Section 5.4.2) are met.
- Persistent or recurrent hematological laboratory abnormalities (see Section 5.5.2).
- Other serious or severe adverse events, at the discretion of the investigator, after consultation with the Medical Monitor.

If a subject withdraws from the study, he/she may request destruction of any samples taken, and the investigator must document this in the site study records.

[figure not shown]
Any subject who withdraws must complete an early withdrawal visit and the 12 week follow-up visit.

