### 4.7.1. Risk Assessment

Potential Risk of Clinical Significance	Summary of Data/Rationale for Risk	Mitigation Strategy
Infections	
Immune-modulating biologic drugs used in RA (such as anti-TNF agents) are associated with an increased risk of serious and opportunistic infections. Similarly, because of the role of GM-CSF in anti-infective immunity, GSK3196165 also has the potential to increase the risk of infection.
 
Non-clinical Data: No changes in peripheral blood populations (lymphocytes, neutrophils, monocytes, eosinophils or basophils), phagocytic activity of peripheral blood polymorphonuclear cells (investigational endpoint in the 26 week study), T-cell dependent B-cell primary or secondary response, or circulating cytokine levels (26 week study) were observed.
 
Studies in knock-out mice showed that GM-CSF deficiency (GM-CSF-/-) affects the ability of mice to control infection when infected with M. tuberculosis or pulmonary group B streptococcus [LeVine, 1999].
 
Clinical Data: One healthy volunteer in study MSC-1000 experienced septic shock secondary to pneumonia 29 days after receiving a single dose of IP at 1.5 mg/kg. Subject recovered after treatment with antibiotics, and the subject completed the study follow-up period as per protocol.
 
One RA subject in study MSC-1001 experienced serious pleurisy which responded to antibiotics.
	
Subject selection (see Section 5.1):
 
 
Subjects with active infections, or a history of recent or recurrent infections are not permitted to enter the study.
 
Subjects with significant leukopenia are not permitted to enter the study.
 
Subjects will be screened for TB, HIV and Hepatitis B and C, and excluded from study participation if positive.
 
Investigators are expected to assess vaccination status, including against influenza and pneumococcus, according to local guidelines.
 
 
Subject monitoring:
 
 
Serious infections and opportunistic infections are categorised as adverse events of special interest (AESIs).
 
Subjects will be monitored for infection similar to subjects receiving any immune-modulating biologic therapy for RA. Appropriate diagnostic tests will be considered during the study if clinically indicated to ensure appropriate safety monitoring.
 
Subjects will be instructed as to the signs and symptoms of infection, and to contact site personnel should they develop. This information will also be contained within the patient Informed Consent Form.
 
 
Withdrawal criteria:
 
 
In the event of a serious or opportunistic infection, study medication should be discontinued and the subject withdrawn from the
 

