Dosing instructions:	
GSK3196165/placebo should be administered on the same day each week <math>\pm</math> 1 day for the first 5 weekly doses (with a minimum of 5 days between doses, for no more than 2 consecutive doses). Following this GSK3196165/placebo should be administered on the same day EOW <math>\pm</math> 3 days (with a minimum of 8 days between doses).
 
GSK3196165/placebo will be discontinued or interrupted as described in Section 5.4 or Section 5.5.
 
Subjects will be randomized as shown in Time and Events Table, Section 7.1, and the dosing schedule should be followed as closely as possible.
 
The unblinded administrator (study co-ordinator or nurse) assigned to the study will be required to prepare and administer the appropriate medication according to the study subject's treatment assignment.
 
Subjects eligible to enter the study will be assigned to treatment randomly through an interactive response technology system (IRTS). Procedures must be in place to ensure the blind is maintained by any site staff involved in clinical care or assessment of the subject, and by the subject themselves.
 
During the first 12 weeks of study every attempt should be made to ensure all doses are administered.
 
After 12 weeks, up to 1 dose in an 8 week period may be missed, not to exceed 2 missed doses total over the 52 weeks of treatment.
 
If at any time the subject misses 2 doses over 52 weeks, the Medical Monitor must be contacted for permission to continue study medication.
	
MTX: can be taken as a single weekly dose, or divided weekly dose, per investigator's discretion.
 
Folic (or folinic) acid should be taken the day after and at least 12 hours following MTX administration.

Physical description:	
Sterile, aqueous solution of purified monoclonal antibody 150 mg/mL
	
Sterile 0.9% (w/v) sodium chloride solution.
 
See label for details

	Study Treatment	Co-medication
Method for individualizing dosage:	
22.5 and 45 mg doses - required volume will be drawn into a small, (e.g. 0.3 or 0.5 mL) syringe.
 
90 and 135 mg doses - required volume will be drawn into a small (e.g. 1 mL) syringe.
 
180 mg dose - required volume will be drawn into a small (e.g. 2 mL or 3 mL) syringe.
 
The required volume should be dosed immediately.
	A volume of 0.6 mL will be drawn into a small (e.g. 1 mL) syringe.

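### Protocol 4.7.1 names opportunistic infection as a withdrawal criterion, but the mandatory withdrawal list in 5.4 names only serious infections; the two must be reconciled

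*Protocol*

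**What the plan says.** Two parts of the protocol say when an infection leads to stopping study medication and leaving the study.

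- **Protocol 4.7.1 (Risk Assessment), infections row, under its withdrawal criteria:** "In the event of a serious or opportunistic infection, study medication should be discontinued and the subject withdrawn". The sentence continues to the word study after a table break. The same row separates the two kinds of event: "Serious infections and opportunistic infections are categorised as adverse events of special interest (AESIs").
- **Protocol 5.4 (Withdrawal/Stopping Criteria):** the list opens with "In addition, study medications will be discontinued and the subject withdrawn from the study in the event of any of the following". Its only infection item is "All serious infections". It ends with a catch-all, "Other serious or severe adverse events, at the discretion of the investigator, after consultation with the Medical Monitor". Earlier in the section, a subject "may be withdrawn at any time at the discretion of the investigator for safety, behavioural or administrative reasons".

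The dosing instructions in Protocol 6.1 say which sections govern stopping: "GSK3196165/placebo will be discontinued or interrupted as described in Section 5.4 or Section 5.5". They do not mention 4.7.1.

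**The concern.** Infection is one of the key potential risks that the protocol names for this antibody (4.7.3), so a site should be able to find one answer to the question of when an infection ends treatment. Here the answer depends on the section consulted. An investigator who follows the dosing instructions reaches 5.4 and finds no entry for opportunistic infection. An investigator who follows the cross-references in 7.4.4.3 or 7.4.6 reaches 4.7.1 and finds that an opportunistic infection calls for withdrawal whether or not it is serious. What is at stake is subject safety and uniform conduct across roughly 70 planned sites (SAP 4.9.1.2).

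**Working it through.** No arithmetic applies. The check is whether the two rules cover the same events and, if not, where they part.

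**Step 1: are the two categories the same?** They are not.

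- Protocol 7.4.6 lists serious infections and opportunistic infections as separate events of special interest, and puts no seriousness condition on the second.
- Protocol 7.4.4.3 speaks of events of special interest, as defined in 4.7.1, that are not serious. The protocol therefore expects such events.
- SAP 4.10.2 (Table 7) derives serious infections from serious adverse events in the infections system organ class. It derives opportunistic infections from the preferred terms in Appendix A with adjudication by the Safety Review Team (SRT), and does not require seriousness.
- Appendix A includes candidate terms such as herpes zoster and oropharyngeal candidiasis, which need not meet a criterion for a serious adverse event.

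**Step 2: apply each rule to each type of infection.**

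| Type of infection | 4.7.1 | 5.4 | Agree? |
|---|---|---|---|
| Serious, opportunistic or not | Discontinue and withdraw | Discontinue and withdraw (mandatory) | Yes |
| Not serious, not opportunistic | No directive | Not on the mandatory list | Yes |
| Opportunistic, not serious, but severe | Discontinue and withdraw | Discretionary, through the catch-all | No |
| Opportunistic, neither serious nor severe | Discontinue and withdraw | General investigator discretion only | No |

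The rules part only in the last two rows, which together are the non-serious opportunistic infections.

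**Step 3: does any other section close the gap?** I found none that does. Section 5.5 covers respiratory symptoms and hematologic abnormalities only. Section 7.4.6 classifies opportunistic infection for reporting and gives no stopping rule. The infections row in 4.7.1 refers to 5.1 for subject selection but gives no reference to 5.4 for withdrawal.

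**Step 4: is the risk table meant to agree with the operative criteria?** The protocol suggests so. The table's other explicit withdrawal entry, for severe hypersensitivity or anaphylaxis, does appear in 5.4. Appendix 12.9 also records that Amendment 3 changed blood-count thresholds in 4.7.1 to match exclusion criterion 25.

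**The case against.** The strongest reply is that nothing in 5.4 conflicts with withdrawing such a subject. Investigator discretion on safety grounds is explicit, so a site that withdraws every subject with an opportunistic infection complies with both sections. The risk table also says should where 5.4 says will. Both points stand, and they limit the finding. A reader might infer that 5.4 orders dosing to continue, or that the sections give opposite commands. The text does not support that: 5.4 leaves the trigger out of a mandatory list. But permission to withdraw is not the same as a direction to withdraw, and a site that keeps the subject on treatment complies with 5.4 while departing from 4.7.1.

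Three further inferences go too far.

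- *That sites will act differently.* The documents show only that they may. Section 4.7.1 is not hidden, since 7.4.4.3 and 7.4.6 lead to it.
- *That every Appendix A term falls into the gap.* The list identifies candidates, the SRT makes the final decision, and the list serves reporting rather than withdrawal at the site. Some listed events would also count as serious under the important-medical-event provision in Appendix 12.4.2, and 5.4 would then apply.
- *That the primary result is biased.* SAP 4.5.2.1 does set visits after early withdrawal to treatment failure for binary endpoints, so a subject's Week 24 status could turn on which section a site followed. But no event rate is given, and investigators are blinded (Protocol 6.5), so a site's reading of the rule would not be expected to favour one arm. An effect is possible but not shown.

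**Conclusion.** The inconsistency is real and narrow. For an opportunistic infection that is not a serious adverse event, 4.7.1 directs discontinuation and withdrawal, and 5.4, which 6.1 makes operative for dosing, leaves the matter at most to the investigator. For all other infections the two sections agree.

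Its size cannot be stated as a number, because the documents give no expected frequency for these events and Appendix A cannot supply one. The conclusion rests on the text of 4.7.1, 5.4, 5.5 and 6.1, and on opportunistic infection not being restricted to serious events, which 7.4.4.3, 7.4.6 and SAP 4.10.2 support. It assumes that the Study Reference Manual and site training materials, which are not among the documents, do not already settle the point. Even if they do, the protocol text should agree with itself. The case for correction is subject safety and uniform conduct, not a demonstrated effect on the primary analysis.

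**What to change.** Reconcile the infections row of 4.7.1 with the list in 5.4 so that both state the same infection-related triggers for discontinuation and withdrawal, with the same force of wording. Which rule applies is for the sponsor's clinical team, and this review takes no position on it. A cross-reference from the withdrawal entries in 4.7.1 to 5.4 would help to keep the two aligned.

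The cost is protocol wording at the next amendment. The sample size, endpoints and planned analyses do not change.
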